**Mindful Self-Compassion Training  
to Improve Retention, Job Satisfaction,  
and Attitudes toward Dementia among  
Long-Term Care Nursing Assistants:  
Certified Nursing Assistants' Wellbeing**

Analysis Overview. Analyses of the intervention’s effectiveness will primarily comprise tests of changes to the outcome measures (see below) from baseline at three post-baseline timepoints: (a) post-intervention, (b) a 3-month follow-up, and (c) a 6-month follow-up. All outcomes were recorded at the same time points within the same self-report survey. Thus, overall, with baseline there were four data collection time points in the study. Secondly, analyses will consider differences in effectiveness by comparing two intervention’s two approaches: (a) the 20-hour intervention delivered in one NH and (b) the 6-hour intervention delivered in two additional NHs. In addition to outcome analyses, participants’ univariate demographic and professional characteristics were calculated to describe the sample (not detailed). Missing data were not imputed, resulting in analyses using listwise deletion of participant observations without data at each time point and for each outcome. Statistical significance was set at  $p < 0.05$  throughout (two-sided) and all analyses were conducted in Stata 16.1.

Primary Outcome. The primary outcome in the study was *Change in Intent to Leave Job*. The specific question asked of participants was “How likely is it that you will leave this job in the next year?” with intent to leave specifically being defined as a “Somewhat likely” or “Very likely” response (1 = Yes) versus a “Not at all likely” response (0 = No). The analysis of the primary outcome proceeded in two steps. First, the descriptive frequencies and percentages of “Yes” and “No” response were calculated for all participants at all four data collection time points to summarize the primary outcome across participants and time. Second, tests for the statistical significance of change from baseline was determined using three sets of McNemar’s exact  $X^2$  tests compared baseline versus the three post-baseline time points. These tests were chosen as appropriate for the (a) non-parametric nature of the data and (b) paired nature of the comparison.

Secondary Outcomes. There were nine secondary outcome domains in the study: (a) mean *Job Satisfaction Scale* (JSS) score; (b) mean *Approach to Dementia Questionnaire* (ADQ) score; (c) mean *Perceived Stress Scale* (PSS) score; (d) mean *PROMIS Depression Scale—Short Form* (PROMIS) score, (e) mean subscale *Maslach Burnout Inventory—Human Services Scale* (MBI) scores; (f) mean total and subscale *Self-Compassion Scale—Youth* (SCS) scores; (g) *Weekly Attendance*; (h) *Number of Days Per Week Spent in Out-of-Class Exercises*; and (i) mean *Satisfaction with Course* score. Briefly, the JSS measured how satisfied participants were with at their job and included 3 individual items (Range: 0–18); the ADQ measured participants’ attitudes toward NH residents with dementia and included 11 items (Range: 0–44); the PSS measured participants’ stress and included 10 items (Range: 0–40); the PROMIS measured participants’ depression levels and included 8 items (8–40); the MBI measured participants’ burnout and included 20 items; the SCS measured participants’ self-compassion and included 17 items; and the study-created *Satisfaction with Course* measure evaluated course-specific satisfaction and included 8 items. Rather than having a total score measuring burnout, the MBI featured 3 subscales related to *Depersonalization*, *Emotional Exhaustion*, and *Reduced Personal Accomplishment* constructs all with a range of 0.0–6.0. The SCS, meanwhile, featured a total score measuring self-compassion along with six subscales related to *Self-Kindness*, *Self-Judgment*, *Common Humanity*, *Isolation*, *Mindfulness*, and *Over-Identification* constructs all with a total range of 1.0–5.0. All scales and sub-scales were summed into unweighted composites of individual items. *Satisfaction with Course* items all had five response options ranging from “Strongly disagree” (1) to “Strongly agree” (5). *Weekly Attendance* was defined as “% of intervention classes fully attended” with a possible score from > 0.0% to 100.0%. Meanwhile, *Number of Days Per Week Spent in Out-of-Class Exercises* was defined as “mean # of days per week over the course of the intervention spent out-of-class doing course mindfulness exercises” with a range from 1.0 to 7.0. The analysis of the secondary outcomes proceeded in three steps. First, the descriptive frequencies, percentages, means, and standard deviations of all measures were calculated for all participants at all four data collection time points to summarize the

secondary outcomes across participants and time. Second, tests for the statistical significance of change from baseline was determined using three sets of either (a) Wilcoxon sign-rank tests for continuous measures or (b) McNemar's exact  $X^2$  tests for nominal measures. These tests were chosen as appropriate for the (a) non-parametric nature of the data and (b) paired nature of the comparisons. Third, change from baseline stratified by intervention approach was determined by comparing the (a) change and (b) significance of the two sub-samples (i.e., 20-hour intervention, 6-hour intervention) for the (a) PSS, (b) PROMIS, and (c) total SCS scores.

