5 STUDY INTERVENTIONS

5.1 Interventions, Administration, and Duration

CNA Wellbeing Program and Measures Intervention

The study will take place over the course of 8 months for each participant – this includes the duration of the intervention as well as follow up measures (see details below).

Before the onset of the intervention, interested participants will complete the Screening Questionnaire, in order to gather their scores on the Perceived Stress Scale. If over 20 CNAs are interested in joining the course, this screening data will be used to choose the 20 CNAs with the highest scores on the Perceived Stress Scale, and invite these participants to join the full study. Otherwise, all eligible CNAs will be included. This Screening Questionnaire will be administered in person, at the recruitment sessions. Alternatively, for CNAs unable to attend the recruitment sessions and who choose to reach out to the study staff directly instead, an option to have a verbal consent and phone version of the Screening Questionnaire will be provided.

Once the final program list has been determined, the study will begin with informed, written consent, and an initial Baseline Interview, no more than 2 weeks before the onset of the course.

The intervention will be administered over the course of 8-weeks for Nursing Home 1, and over the course of 6-weeks for Nursing Home 2 & 3, and follows the pre-created agenda for the Mindful Self-Compassion course (see below, Table 2). Participants will be texted weekly by study staff, with reminders of the next session, as well as a recap of the previous session. At the beginning of the course, study staff will collect Weekly Questionnaires on each participant. This will be given by the intervention instructors during the sessions. If a participant has missed a session, study staff will follow up to collect a modified Weekly Questionnaire by phone. Towards the end of the course, a half-day (4 hour) retreat was offered to participating CNAs (of Nursing Homes 1). They were encouraged to attend this retreat, however, it was not required and attendance (or non-attendance) did not impact their participation in the study. Ultimately, the retreat was not held due to difficulties with scheduling.

No more than two weeks after the termination of the course, study staff will administer an End-of-Program Interview either in person or via telephone, according to the convenience of the participant.

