10.3 Reimbursement Schedule for Participants

Each component of the study is associated with a separate compensation (refer to Table 3), and is a nominal, non-coercive amount, to reflect the time that they will be dedicating to the study.

The CNA Wellbeing Program is being administered in two different forms of the intervention:

1. Nursing Home 1 will have the standard, MSC program (8 weeks, 2.5 hours per week) administered
2. Nursing Home 2 & 3 will have the modified, MSC program (6 weeks, 1.25 hours per week)

The original compensation of \$180 was awarded to persons in the NH #1, 8-week program, in which they were reimbursed \$25 per interview, and \$10 per class (\$25 x 4, \$10 x 8 = \$180). This equates to \$5.00 per 1.25 hours of class, and \$25.00 per interview. This reimbursement amount & schedule was changed after Nursing Home #1, after receipt of feedback from participants that the reimbursement was not commensurate to their time dedicated to the project. We also readjusted our reimbursement schedule in response to feedback – rather than waiting until the end of the intervention to reimburse participants for the first time, we added in a mid-intervention reimbursement point.

In response to feedback, the compensation per time spent in class doubled. For those in the 6-week, 1.25 hour-Program, participants will be reimbursed a total of \$140. This includes \$80 in participation in all 4 interview (\$20 each), and \$60 for their participation in 7.5 hours of intervention (\$10 per 6, 1.25 hours classes).

Table 3A – Reimbursement Payments/Schedule (for 2.5 Hour, 8-Week Program)		
Study Component	Reimbursement Amount	Schedule
Baseline Interview	\$20.00	Reimbursed once: 1. After End of Program (up to \$100)
Weekly Questionnaire	\$20/per class/questionnaire	
End-of-Program Interview	\$20.00	
3-Month Interview	\$20.00	To be reimbursed after completion of 3-Month Interview (up to \$20)
6-Month Interview	\$20.00	To be reimbursed after completion of 6-Month Interview (up to \$20)

Table 3B – Reimbursement Payments/Schedule (for 1.25 Hour, 6-Week Program)		
Study Component	Reimbursement Amount	Schedule
Baseline Interview	\$20.00	To be reimbursed twice: 1. After mid-way point (week 3) of program (up to \$50) 2. After End of Program (up to \$50)
Weekly Questionnaire	\$10/per class/questionnaire	
End-of-Program Interview	\$20.00	
3-Month Interview	\$20.00	To be reimbursed after completion of 3-Month Interview (up to \$20)

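### The 20-hour versus 6-hour comparison is fully aliased with nursing home and study phase, and payment changed too, so it can only be descriptive

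*SAP*

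**What the plan says.** The SAP's Analysis Overview states that "analyses will consider differences in effectiveness by comparing two intervention’s two approaches", namely "a) the 20-hour intervention delivered in one NH and (b) the 6-hour intervention delivered in two additional NHs". The third step under Secondary Outcomes gives the method: "change from baseline stratified by intervention approach was determined by comparing" the size of the change and its significance in the two sub-samples, for PSS, PROMIS and total SCS. No direct between-version test is described, and there is no term for home, phase or payment.

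The protocol fixes version by home. Section 5.1 delivers the course "over the course of 8-weeks for Nursing Home 1, and over the course of 6-weeks for Nursing Home 2 & 3". Section 3 calls the trial single-arm and places the refined version after the first home, with 15 participants planned in home 1 and 15 in each of homes 2 and 3.

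Section 10.3 says that payment amount and schedule were changed after home 1: "In response to feedback, the compensation per time spent in class doubled". A mid-programme payment was also added.

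Neither document says that these factors move together or limits how the comparison may be read.

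**The concern.** A contrast presented as a difference in effectiveness will be read as a statement about the two programmes. Here, anything that distinguishes home 1 from homes 2 and 3, or the first phase from the second, produces the same contrast. Examples are staff mix, management, calendar time, lessons learnt in the first phase, and payment. A reader could conclude that the short course works as well as, better than or worse than the long one when the data show only that the homes differed.

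The side-by-side use of significance is a separate weakness. The short-version group is planned at twice the size, so the same true change is more likely to reach p < 0.05 there. A pattern of significant in one group and not significant in the other is not evidence that the changes differ.

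**Working it through.** **1. Aliasing.** Inputs are the allocation in protocol section 5.1 and the planned 15 per home in section 3. Let V = 1 for the long version, and let H2 and H3 indicate homes 2 and 3. Then V = 1 − H2 − H3 for every participant.

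- A model with an intercept, H2 and H3 has rank 3. Adding V leaves it at 3, and adding phase and payment rate also leaves it at 3.
- A model with an intercept and V has rank 2. Adding phase and payment rate leaves it at 2.

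No covariate adjustment, test or interval can therefore isolate version.

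**2. Comparing significance.** Assumptions: 15 and 30 completers, the same true standardised change d in both groups, two-sided 5%, and a paired t test as a stand-in for the Wilcoxon test. The documents give no value for d, so a range is shown. P(exactly one significant) = p15(1 − p30) + p30(1 − p15).

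| d (assumed) | power, n = 15 | power, n = 30 | exactly one significant |
|---|---|---|---|
| 0.3 | 0.192 | 0.355 | 0.41 |
| 0.5 | 0.438 | 0.754 | 0.53 |
| 0.7 | 0.713 | 0.959 | 0.30 |

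**3. Payment (section 10.3).** The text's totals reproduce: 25×4 + 10×8 = $180 for home 1, and 20×4 + 10×6 = $140 for homes 2 and 3. So does the doubling: 10/2.5 = $4 per class hour against 10/1.25 = $8.

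"Table 3A – Reimbursement Payments/Schedule (for 2.5 Hour, 8-Week Program") does not agree with that text. Its rates are $20 per interview and $20 per class.

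| Home 1 | text | Table 3A rates |
|---|---|---|
| Total | $180 | 20×4 + 20×8 = $240 |
| Due by end of programme (stated cap $100) | 25×2 + 80 = $130 | 20×2 + 160 = $200 |
| Per class hour | $4 | 20/2.5 = $8 |

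The $100 cap fits neither column. On either column, total pay and payment timing differ from homes 2 and 3. Whether the hourly rate differed depends on which column is right and on class length, because homes 2 and 3 received $8 per hour at 1.25-hour classes but $10 at 1-hour classes.

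**4. Size of the contrast in hours.** The long version is 8 × 2.5 = 20 hours, as labelled. The précis gives the short version as 6 × 1 = 6 hours, but section 10.3 gives 6 × 1.25 = 7.5. The ratio of hours is 20/6 = 3.3 or 20/7.5 = 2.7.

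**5. Illustration only: a direct test that the SAP does not plan.** Assume no version effect, unit SD, 15 per home and an intraclass correlation ρ of change scores by home (not in the documents). The naive variance is 1/15 + 1/30 = 0.10. The true variance is (1 − ρ)(0.10) + 1.5ρ = 0.114, 0.170 or 0.240 for ρ = 0.01, 0.05 or 0.10. The size of a nominal 5% test that ignores home is 2P(Z > 1.96√(0.10/true variance)) = 0.066, 0.133 or 0.206.

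**The case against.** The strongest reply is that this is a feasibility study and the comparison is secondary. The SAP sentence itself discloses one home against two. Protocol section 4 restricts the homes on quality rating, bed size, non-profit status and distance, and section 5.2 names one instructor pair. All of that stands. It limits how large home differences may be and how much the comparison matters, but it leaves version and home inseparable. Running two versions in sequence is a legitimate pilot design and is not criticised here.

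Several stronger readings go further than the documents allow:

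- **Inflated error rate.** A reader might take 7%, 13% or 21% as the plan's false-positive rate. Those figures belong to a direct test that the SAP does not specify, under an assumed intraclass correlation.
- **Choice of version for the future trial.** Neither document says that this comparison makes that choice. Sections 1.1 and 3 have feedback from home 1 refine the course before the comparison exists.
- **Changed recruitment.** Section 1.1 states an intention to modify recruitment. Section 4.2 gives a single recruitment schedule and describes no actual change between phases.
- **Better-paid participants in homes 2 and 3.** On the text, pay per class hour rose, but pay per interview fell from $25 to $20 and the total from $180 to $140. On Table 3A the hourly rate is unchanged at 1.25-hour classes.
- **Home 2 versus home 3 as a yardstick.** This is one contrast with 15 per home. Under the model in step 5, sampling noise, 2(1 − ρ)/15, against true home variation, 2ρ, makes up about 87%, 56% or 38% of its variance. A small gap would not show that homes are alike.

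**Conclusion.** The concern holds in a limited form. The contrast between versions is completely aliased with home and phase. Payment amount and timing also changed after home 1, although the size of the hourly change is unsettled. Neither a difference in change nor a difference in significance can be attributed to programme version. The aliasing follows from the allocation alone and needs no assumption. The 41%, 53% and 30% figures rest on the planned numbers, equal true changes and a t-test approximation. Listwise deletion or different enrolment would alter them, but the fault in comparing p-values would remain.

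The consequence is moderate. It concerns what may be concluded from three secondary scales, and leaves the primary analysis of intent to leave untouched. The conflicts over Table 3A and class length are side corrections. They matter here because they describe what differed between the versions.

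**What to change.** In the third step of the SAP's Secondary Outcomes:

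1. Report change from baseline, with its SD or a confidence interval and the number analysed, for PSS, PROMIS and total SCS separately for each of the three homes.
2. Drop the comparison of significance between sub-samples.
3. In the Analysis Overview, replace the aim of comparing effectiveness with a statement such as: Results are described by home; programme version, home, study phase and payment regime cannot be separated, and no difference will be attributed to version.
4. Show home 2 beside home 3 as context only, not as an estimate of between-home variation.

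As side corrections in the protocol, reconcile Table 3A with the text of section 10.3 against what was actually paid, and reconcile the stated session lengths with the 6-hour label.

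The cost is a few sentences and one three-column table from data already held. The conclusion about the two versions becomes more modest.

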1.2 Aim 2 Objective

Conduct a pilot test of the adapted protocols and intervention in a sample of 30 CNAs from 2 similarly rated and structured community NHs to reexamine feasibility and acceptability, identify trends in key intermediate and long-term outcomes, and estimate effect size in preparation for a future randomized trial.

- A.** Evaluate the fidelity and immediate impact of the modified training by measuring (a) training attendance; (b) satisfaction with the training; and (c) pre-and post-training measures of self-compassion, perceived stress, job satisfaction, job burnout symptoms, and attitudes towards persons with dementia.
- B.** Evaluate the sustained impact of the training by comparing baseline, 3-and 6-month post-training measurements of: intent to leave job, self-compassion, perceived stress, job satisfaction, job burnout symptoms, and attitudes towards persons with dementia.

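### Displayed baseline and follow-up values can come from different participants, and no full-sample within-person change is planned, so selective drop-out alone can shift the apparent effect

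*SAP*

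**What the plan says.** The Analysis Overview of the SAP states that "Missing data were not imputed", "resulting in analyses using listwise deletion of participant observations without data at each time point and for each outcome".

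The primary outcome, intent to leave, is handled in two steps. First, frequencies and percentages "were calculated for all participants at all four data collection time points to summarize the primary outcome across participants and time". Second, each of the three follow-ups is compared with baseline by an exact McNemar test, chosen partly for the "paired nature of the comparison".

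The secondary scales follow the same pattern. The "means, and standard deviations of all measures were calculated for all participants at all four data collection time points", and change from baseline is then tested at each follow-up with Wilcoxon signed-rank tests. A third step compares change between the 20-hour and 6-hour approaches for the PSS, PROMIS and total SCS scores. It does not say whether that change is within-person or a difference between visit means.

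The SAP names no baseline summary restricted to the tested pairs, no number of pairs, no full-sample estimate of within-person change, and no comparison of participants with and without follow-up data. Protocol section 1.2 gives as one purpose of Aim 2 to "estimate effect size in preparation for a future randomized trial". Protocol section 3 describes a single-arm study.

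**The concern.** Without imputation, a visit summary can include only people with data at that visit. The baseline column would then contain participants who are missing from later columns and from the tests. For the full sample, the tests are described only as tests of statistical significance. The visit means and percentages are therefore the only effect sizes the plan puts on display for the whole sample.

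With no control arm, nothing offsets a change in who is being summarised. If the people lost differ at baseline from those kept, the displayed values move from baseline to follow-up even when nobody has changed. A planner who subtracts one column from the other to size the next trial would carry that shift forward. The primary outcome is as exposed as the scales: it concerns leaving the current job, and the SAP gives no rule for a participant who has already left by a follow-up visit.

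**Working it through.** **Inputs.** The planned sample is 45: 15 in the first home and 30 in the other two (Protocol section 3). This is a goal; up to 20 per home are allowed, so the maximum is 60. The PSS ranges from 0 to 40 (SAP, Secondary Outcomes). The documents give no expected drop-out, SD, baseline percentage or effect size, so there is no stated figure to reproduce. Every loss rate and baseline difference below is an assumption, and no participant truly changes.

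**Scales.** Let f be the fraction lost, and let L and R be the baseline means of lost and retained participants.

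- Displayed baseline mean = (1 − f)R + fL.
- Displayed follow-up mean = R.
- Displayed change = R − [(1 − f)R + fL] = −f(L − R).

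Size of the shift:

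- L = R: 0 at any loss rate.
- 0.5 SD difference, 20% lost: 0.2 × 0.5 = 0.10 SD.
- 0.5 SD difference, 40% lost: 0.4 × 0.5 = 0.20 SD.
- PSS, 4-point difference: 0.1 × 4 = 0.4, 0.2 × 4 = 0.8 and 0.3 × 4 = 1.2 points at 10%, 20% and 30% lost.

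The shift looks like improvement if worse-scoring participants are lost, and like deterioration of the same size if better-scoring ones are.

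**Intent to leave.** Let p be the baseline proportion answering Yes, and dY and dN the loss rates among Yes and No participants. Displayed follow-up proportion = p(1 − dY) / [p(1 − dY) + (1 − p)(1 − dN)].

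Take p = 0.5, 20% lost overall, and Yes participants lost twice as often. Then dN = 0.2/1.5 = 0.133, dY = 0.267, and the displayed proportion is 0.5 × 0.733/0.8 = 0.458, a fall of 4.2 points. Other cases:

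| Baseline Yes | Overall loss | Yes lost twice as often | Equal loss | No lost twice as often |
|---|---|---|---|---|
| 50% | 20% | −4.2 points | 0 | +4.2 points |
| 50% | 40% | −11.1 points | 0 | +11.1 points |
| 30% | 20% | −4.0 points | 0 | +3.1 points |
| 30% | 40% | −10.8 points | 0 | +8.2 points |

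**Example in counts (assumed).** Of 45 at baseline, 20 answer Yes (44.4%). If 8 Yes and 3 No participants are lost, the display runs from 20/45 = 44.4% to 12/34 = 35.3%, an apparent fall of about 9 points. If 3 Yes and 8 No participants are lost instead, it runs from 44.4% to 17/34 = 50.0%, an apparent rise of 5.6 points. In both cases the 34 pairs contain no discordant answers, so the paired change is 0 and the exact McNemar p is 1.

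**Check on the tests.** A simulation used 45 participants, 2,000 runs per setting, an assumed PSS mean of 18 and SD of about 5.8, no true change, and loss depending on each person's stable stress level.

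| Loss pattern | Loss | Displayed difference | Paired difference | Wilcoxon rejection |
|---|---|---|---|---|
| Higher stress lost more | 24% | −1.05 | −0.01 | 5.0% |
| Higher stress lost more | 33% | −1.38 | 0.02 | 5.3% |
| Unrelated to stress | 20% | 0.02 | 0.01 | 4.4% |
| Unrelated to stress | 30% | −0.01 | −0.01 | 5.0% |
| Lower stress lost more | 24% | +1.04 | 0.02 | 6.1% |
| Lower stress lost more | 33% | +1.38 | −0.01 | 4.2% |

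The displayed difference moves with the loss pattern. The paired difference stays near zero and rejection stays near the nominal 5%.

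**The case against.** The strongest reply has three parts.

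- **The mismatch is an inference.** The SAP never says that the summaries use everyone with data at a visit. Its deletion sentence speaks of analyses in general. If complete data at all four visits were also required for the summaries, the summary and test sets would coincide and the shift would vanish. That reading is hard to square with summaries of all participants, but the SAP leaves the point open. It should state the set.
- **The effectiveness analysis is paired.** The Analysis Overview makes tests of change its main component, and these are not distorted by the change in composition. This stands. The tests do describe only those retained, and they could still mislead if loss depended on the change itself.
- **Loss may be small.** Section 5.3 of the Protocol keeps following participants whatever their adherence, section 9.1 allows telephone interviews within two weeks either side of the follow-up date, and section 10.3 pays for each follow-up interview. These measures limit loss but do not exclude it.

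It is also fair to say that nothing prevents the team from reporting matched baselines, and that the effect-size aim concerns the 30 participants of Aim 2, not all 45. Neither point supplies the missing estimate: the plan does not name it, and only the third step, for three scores, mentions change by approach.

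**Conclusion.** The point holds for the displayed summaries. On the natural reading, the baseline and follow-up figures can describe different participants, and the plan offers no full-sample within-person change in their place. In the illustrations the shift runs from zero to 0.20 SD for a scale, and to about 11 points for intent to leave at 40% loss with a two-to-one loss ratio. It may go in either direction. These sizes rest entirely on assumed loss rates and differences.

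Four stronger conclusions that a reader might infer are not supported:

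- *That the tests are invalid.* The paired comparisons are not shifted by this mechanism.
- *That the bias must be favourable.* The conceptual model in Protocol section 2 links stress to absenteeism and turnover, which makes loss of worse-scoring participants plausible. It says nothing about missed study interviews.
- *That about 40% will be lost.* The 65% in section 2 is annual national job turnover. Converting it at a constant rate gives 1 − 0.35^(6/12) = 41% over six months or 1 − 0.35^(8/12) = 50% over the eight months of participation. Neither is study drop-out, and leaving the job is not stated to end follow-up.
- *That anyone missing one visit is removed from every comparison.* The deletion sentence refers to each time point and outcome, and three separate paired tests are planned, so deletion within each comparison is the better reading.

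This is a worthwhile and inexpensive improvement. It does not overturn any planned test.

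**What to change.** 1. State in the Analysis Overview that each comparison uses every participant with a baseline value and a value at that visit, and state which participants enter the visit summaries.
2. For intent to leave and each scale, at each follow-up, report the number of pairs, the baseline value in those same participants, the follow-up value and the within-person change. For intent to leave, give the paired 2×2 counts. In the first example above these would be 12 Yes–Yes, 22 No–No and no discordant pairs, so 35.3% at both visits and a change of 0.
3. Add one table of baseline values for participants with and without 6-month data, so that the reader can judge whether loss was related to score and in which direction.

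The cost is a few sentences in the SAP, some extra columns and one small table, all from data already collected. The downside is a longer results table.
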